5.3.2.2. Time to Event Endpoints

The following endpoints will be analysed using time to event analyses with a follow-up to Day 60:

- Time to all-cause mortality
- Time to first discharge from investigator site
- Time to first discharge to non-hospitalised residence

The following exploratory endpoints will be analysed using time to event analyses with a follow-up to Day 28:

- Time to recovery from respiratory failure
- Time to last dependence on supplementary oxygen
- Time to final ICU discharge

For time to event endpoints where the event is a worsening participant status, participants with missing data due to study withdrawal prior to occurrence of the event will be censored at the time of study withdrawal, participants alive at the end of follow-up will be censored at the time of end of follow-up (i.e. Day 28/60).

For time to event endpoints where the event is an improvement participant status, participants with missing data due to study withdrawal prior to first occurrence of the event will be censored at the time of end of follow-up. The end of follow up will be the earliest of the nominal timepoint (i.e. Day 28/60) and their actual study day of visit. If a participant meets the endpoint at the point of withdrawal, then the participant will be assumed to have achieved the event.

The endpoint will be analysed using a Cox proportional hazards model adjusted by treatment, clinical status and age group at baseline. Ties will be broken using Efron's method. The hazard ratio of the treatment group and corresponding confidence interval and p-value will be reported. For any endpoint where a hazard ratio above 1 indicates improvement of otilimab over placebo, the inverse hazard ratio will also be presented. For model checks refer to Section 6.3.3.

Kaplan-Meier plots will be presented by treatment group. Estimates of the median time-to-event and other relevant percentiles will be derived from the unadjusted Kaplan-Meier plots and reported in a table. If 50% of participant do not meet the event definition during the study, alternative percentiles may be produced.

Kaplan-Meier plots will be presented by treatment group.

Additionally, for time to ICU discharge, the following summaries will be produced:

- For participants who are in the ICU at any point during the trial, the duration of ICU stay will be summarised separately for participants that have died and those that complete the study, it will be further split by participants ICU status (in ICU at dosing or entered ICU post-dose).
- Additionally, for all participants a count and proportion of participants with stays in the ICU of 0 days, 1-<7 days, 7-<14 days and ≥ 14 days will be produced.

5.3.3. Sensitivity Analyses

5.3.3.1. Binary Endpoints

Sensitivity analyses as per Section 5.2.3 will be performed on the binary endpoints in the hierarchy specified in Section 2.1 (Participants alive and free of respiratory failure at Day 14, All-cause mortality at Day 60). Sensitivity analyses on additional endpoints may be investigated, further details will be provided in a separate technical document.

5.3.3.2. Time to Event Endpoints

As a sensitivity to the competing risk of death an alternative model will be investigated to analyse the time to event endpoints in the hierarchy specified in Section 2.1 (time to recovery from respiratory failure up to Day 28). Analysis will be performed as follows:

- Competing risks via Fine-Gray method will be conducted. The competing risk for time to recovery from respiratory failure will be death. The model will be adjusted for clinical status and age group. In this case, the hazard ratio of the treatment group and corresponding confidence interval and p-value will be reported.

Sensitivity analyses on additional endpoints may be investigated, further details will be provided in a separate technical document.

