1.2.2. Estimands

Each study objective is presented below with additional information, including prespecified estimands with related attributes.

Table 3 **Estimands**

Estimand Category	Estimand			
	Variable/Endpoint	Population	Intercurrent Event Strategy	Treatment Comparison
Primary Objective: To compare the efficacy of otilimab 90 mg IV versus placebo				
Primary	Participants alive and free of respiratory failure at Day 28	Entire trial population randomised and receiving treatment (MITT)	Data analysed as collected (treatment policy strategy)	Odds ratio and difference in proportions
Secondary Objective: To compare the efficacy of otilimab 90 mg IV versus placebo.				
Secondary 1	All-cause mortality at Day 60	Entire trial population randomised and receiving treatment (MITT)	Data analysed as collected (treatment policy strategy)	Odds ratio and difference in proportions
Secondary 2	Time to all-cause mortality up to Day 60	Entire trial population randomised and receiving treatment (MITT)	Data analysed as collected (treatment policy strategy)	Hazard ratio
Secondary 3	Participants alive and free of respiratory failure at Day 7, 14, 42, and 60	Entire trial population randomised and receiving treatment (MITT)	Data analysed as collected (treatment policy strategy)	Odds ratio and difference in proportions
Secondary 4	Time to recovery from respiratory failure up to Day 28	Entire trial population randomised and receiving treatment (MITT)	Participants who die will be censored at end of follow-up (composite strategy) For all other intercurrent events, the data will be analysed as collected (treatment policy strategy)	Hazard ratio

Estimand Category	Estimand			
	Variable/Endpoint	Population	Intercurrent Event Strategy	Treatment Comparison
Secondary 5	Participants alive and independent of supplementary oxygen at Day 7, 14, 28, 42, and 60	Entire trial population randomised and receiving treatment (MITT)	Data analysed as collected (treatment policy strategy)	Odds ratio and difference in proportions
Secondary 6	Time to last dependence on supplementary oxygen up to Day 28	Entire trial population randomised and receiving treatment (MITT)	Participants who die will be censored at end of follow-up (composite strategy) For all other intercurrent events, the data will be analysed as collected (treatment policy strategy)	Hazard ratio

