5.3.1. Endpoint Definition

5.3.1.1. All-cause Mortality at Day 60

Participants will meet the endpoint if they have died due to any cause prior to Day 60.

If the date of death is unknown refer to Section [5.1.5](#) for missing data handling rules.

5.3.1.2. Time to All-cause Mortality up to Day 60

Defined as the time (days) from dosing to death, due to any cause, up to (and including) Day 60.

5.3.1.3. Participants Alive and Free of Respiratory Failure at Day 7, 14, 42, and 60

Defined as per primary endpoint, see Section 5.2.1.

5.3.1.4. Time to Recovery from Respiratory Failure up to Day 28

Defined as the time (days) from dosing to last recovery from respiratory failure up to (and including) Day 28. Participants are in respiratory failure if they are in category 5 or above from the GlaxoSmithKline (GSK) modified ordinal scale adapted from World Health Organization (WHO) scale 2020 (Table 4).

Note: if a participant has recovered from respiratory failure but then progresses back into respiratory failure on or prior to the end of follow up (Day 28) the participant has not had their last recovery from respiratory failure.

This endpoint will use a composite approach for death such that if the intercurrent event of death occurs (on or prior to Day 28), then time will be censored at end of follow up (Day 28).

5.3.1.5. Participants Alive and Independent of Supplementary Oxygen at Day 7, 14, 28, 42, and 60

Participants are independent of supplementary oxygen if they are in category 1, 2 or 3 from the GlaxoSmithKline (GSK) modified ordinal scale adapted from World Health Organization (WHO) scale 2020 (See Table 4- Ordinal Scale). Alternatively, if the ordinal scale is unknown but ventilation or oxygen status is available, then the endpoint is defined as the first full day where oxygen support is not required.

Participants will meet the endpoints if they are alive and independent of supplementary oxygen at Day 7, 14, 28, 42, and 60 respectively. As participants may be discharged from investigator site prior to Day 28, analysis windows will be used to define the endpoint, further details on analysis windows will be provided in the Output and Programming Specification (OPS).

5.3.1.6. Time to Last Dependence on Supplementary Oxygen up to Day 28

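### Part 1's Fine-Gray sensitivity analysis of time to recovery essentially repeats the main Cox analysis, so it cannot show sensitivity to how death is handled

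*SAP*

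**What the plan says.** All references are to the Part 1 SAP unless stated.

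- **Estimand (Section 1.2.2, Table 3).** For time to recovery: "Participants who die will be censored at end of follow-up (composite strategy".
- **Endpoint (Section 5.3.1.4).** The event is the last recovery up to Day 28, and "if the intercurrent event of death occurs (on or prior to Day 28), then time will be censored at end of follow up (Day 28". Someone who recovers and then dies by Day 28 therefore has no event.
- **Withdrawals (Section 5.3.2.2).** For endpoints that represent improvement, participants who withdraw "prior to first occurrence of the event will be censored at the time of end of follow-up". The next sentence qualifies this: "The end of follow up will be the earliest of the nominal timepoint" and the actual study day of the visit.
- **Main model (Section 5.3.2.2).** "Cox proportional hazards model adjusted by treatment, clinical status and age group at baseline", and "Ties will be broken using Efron's method".
- **Sensitivity model (Section 5.3.3.2).** "As a sensitivity to the competing risk of death an alternative model will be investigated to analyse the time to event endpoints". The model is Fine-Gray, with death as the competing event, adjusted for clinical status and age group, and reporting the treatment hazard ratio. No tie method, variance formula or withdrawal rule is given for it.

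Section 5.3.3.2 identifies time to recovery as part of the testing hierarchy. Fine-Gray is the only time-to-event sensitivity analysis specified there.

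**The concern.** A sensitivity analysis is informative only if it changes the assumption it is meant to probe. Here that assumption is the treatment of death. A standard Cox analysis would censor people when they die, and Fine-Gray would then be a real alternative. This main analysis does not do that: it holds deaths at risk to Day 28, which is the defining feature of the Fine-Gray risk set.

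The report would then show two matching hazard ratios, one labelled as sensitivity to the competing risk of death. A reader would naturally take the match as evidence that the recovery result does not depend on how death is handled, when the match is built into the method. It matters because a reduction in deaths can by itself raise the recovery hazard ratio above 1 with no faster recovery among those alive, and neither planned model can separate the two.

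**Working it through.** The plan states no figure to reproduce, so the check is algebraic, then numerical.

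**Step 1: compare the risk sets.** Let t be a day up to Day 28.

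- Main Cox: at risk on day t is everyone without a last recovery before t. Deaths are included, because their time is set to Day 28.
- Fine-Gray: at risk is everyone event-free and uncensored at t, plus everyone who died at an earlier day D, with weight w(t) = G(t)/G(D). G is the Kaplan-Meier estimate of remaining uncensored.

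If nobody is censored before Day 28, G = 1 throughout and w(t) = 1/1 = 1. Events, risk sets and covariates coincide, so the partial likelihood and the hazard ratio are the same. This needs no assumption about event rates.

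**Step 2: numerical check.** The Part 1 size is 806 (Protocol, summary of changes for Amendment 3). The Protocol (Section 8.4.2) expects little missing data but gives no rate, so withdrawal was assumed at 0%, 3% and 10%. Recovery and death rates were also assumed. The set-up was 1:1 allocation, daily event times, the SAP covariates, a death hazard ratio of 0.8 or 0.4, and 30 data sets per setting.

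In one data set without withdrawal, main Cox and Fine-Gray both gave a log hazard ratio of 0.13640649 (HR 1.1461). The model standard error was 0.11558 and the robust one 0.11549.

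Change in log hazard ratio from the main Cox analysis, across all settings:

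| Analysis | Change |
|---|---|
| Fine-Gray, SAP censoring rules, Efron ties | 0 in every data set |
| Fine-Gray, Breslow ties | at most 0.005 |
| Fine-Gray, withdrawals censored at withdrawal and weighted | at most 0.020 (3%), 0.023 (10%) |
| Plain Cox, deaths held to Day 28, withdrawals censored at withdrawal | at most 0.019 (3%), 0.025 (10%) |
| Cause-specific Cox, death HR 0.8 | mean about -0.03, largest 0.09 |
| Cause-specific Cox, death HR 0.4 | mean -0.12 to -0.13, largest 0.20 |

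The third and fourth rows show that the small Fine-Gray shift comes from the withdrawal rule. In one data set with 10% withdrawal, main Cox gave 0.10229, weighted Fine-Gray 0.09898 and the plain Cox with the same withdrawal rule 0.09911. The last two differ by 0.09911 - 0.09898 = 0.00013. Cause-specific Cox gave 0.08838.

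**Step 3: the early-visit clause.** With 20% of non-events censored at Day 26 or 27, the death hazard multiplied by 0.6 and no effect on recovery (806 participants, 60 data sets), the largest gap between main Cox and Fine-Gray was 0.0017 on the log scale. Average hazard ratios were 1.10 (main), 1.10 (Fine-Gray) and 0.99 (cause-specific). A separate run with 800 participants and the same death effect (300 replicates) gave 1.13 for main and Fine-Gray, and 1.00 for cause-specific. The size depends on the assumed rates; the pattern does not change.

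**Step 4: recovered, then died.** Counting these participants as recoveries in the Fine-Gray run moved the log hazard ratio by up to about 0.11. That would change the endpoint and contradict Section 5.3.1.4, so it does not rescue the planned analysis.

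**The case against.** Four counter-arguments deserve an answer.

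**The two models need not match exactly.** A reader might infer that Fine-Gray can never give a different number. The documents do not support that. End of follow-up can fall on a visit before Day 28, where weights may drop below 1, and the tie, variance and withdrawal rules for Fine-Gray are unstated. This stands, but the resulting shifts are about 0.02 or less and do not arise from the handling of death.

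**Mortality is reported elsewhere.** A reader might infer that nobody could tell faster recovery from fewer deaths. That goes too far. Part 1 plans all-cause mortality at Day 60, a Cox hazard ratio for death with Kaplan-Meier plots (Section 5.3.2.2), and daily status charts that include death (Section 5.2.2). What is missing is a cause-specific recovery hazard ratio and paired cumulative incidence curves.

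**Death is meant to count against recovery.** The composite strategy is deliberate, and the Part 2 SAP (Section 1.1.2) gives a reasonable rationale for it. A mortality contribution to the recovery hazard ratio is therefore intended. A cause-specific hazard ratio answers a different question and is supplementary. This stands, and it is why the main analysis should stay.

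**The reach is small.** This is one run on one secondary endpoint, tested only if the primary null hypothesis is rejected (Section 2.1). The Part 2 SAP has no Fine-Gray analysis: its Section 4.3.3.2 extends follow-up to Day 60 instead. Part 1's Day 28 primary and mortality data had been analysed before Protocol Amendment 3. All of this limits the consequence, but the label in Section 5.3.3.2 is still wrong.

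**Conclusion.** The point holds in a limited form. The Fine-Gray run in Section 5.3.3.2 essentially duplicates the main Cox analysis and cannot show sensitivity to the handling of death. Equality of the hazard ratios is exact when nobody is censored before Day 28. Otherwise the difference was at most 0.023 on the log scale in the settings tried, and it came from ties or censoring rules.

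The contrast that does vary the handling of death moved the log hazard ratio by about 0.03 on average with a death hazard ratio of 0.8, a factor of exp(0.03) = 1.03. With a death hazard ratio of 0.4 it moved by 0.12 to 0.13, a factor of 1.13 to 1.14. These sizes rest on assumed recovery, death and withdrawal rates; the equivalence itself does not.

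A reader might infer that the main recovery analysis is biased or that the primary result is in doubt. Neither follows. The composite estimand is legitimate, the redundant run biases nothing, and the primary endpoint is not touched. The fault is that agreement between the two models would be presented as evidence it cannot provide.

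**What to change.** 1. In the Part 1 SAP or the study report, state that the main hazard ratio for time to recovery is in effect a subdistribution hazard ratio and that Fine-Gray is equivalent to it. Do not report their agreement as robustness to death.
2. Add, as a supportive contrast, a cause-specific Cox model that censors at the date of death, with the same covariates and tie method as the main model.
3. Show cumulative incidence curves for recovery and for death by arm, and read them with the mortality hazard ratio already planned.
4. Mark the additions as post hoc if they are made after unblinding.

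The cost is a few sentences, one model and one figure, all from data already collected. The downside is that the cause-specific hazard ratio conditions on being alive, so it is supportive only and should not replace the main estimate or enter the testing hierarchy.

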5.3.4. Supplementary Analyses

Supplementary estimands as described in Section 5.2.4 may be performed.

5.3.5. Subgroup Analyses

Subgroup analyses may be performed as per Section 5.2.5 and will use the methods described above.

5.4. Exploratory Endpoint(s) Analyses

Exploratory endpoints may be analysed at the final analysis only.

5.4.1. Definition of Endpoint(s)

5.4.1.1. Invasive Mechanical Ventilation (if not previously initiated) up to Day 28

Participants will meet the endpoint if they have had invasive mechanical ventilation initiated up to (and including) Day 28. This will only be evaluated for participants who are not supported using invasive mechanical ventilation at baseline.

Participants who die on or prior to Day 28 without the initiation of invasive mechanical ventilation will be considered to have met the endpoint (composite estimands strategy).

5.4.1.2. Time to Invasive Mechanical Ventilation (if not previously initiated) up to Day 28

Time from dosing (days) to first use of invasive mechanical ventilation or death up to (and including) Day 28 as defined in Section 5.4.1.1. This will only be evaluated for participants who are not supported using invasive mechanical ventilation at baseline.

This endpoint will use a composite approach for death such that for participants who die on or prior to Day 28 without the initiation of invasive mechanical ventilation, the time to invasive mechanical ventilation will be set as the time of death.

5.4.1.3. Alive and Not Invasively Mechanically Ventilated up to Day 28

Participants will meet the endpoint if they are alive and not requiring invasive mechanical ventilation at Day 28. This will be evaluated only for participants supported using invasive mechanical ventilation at baseline

5.4.1.4. Time to Definitive Extubation up to Day 28

For participants supported using invasive mechanical ventilation at baseline this is defined as the time from dosing (days) to final extubation from invasive mechanical ventilation up to (and including) Day 28.

This endpoint will use a composite approach for death such that if the event has not occurred prior to the intercurrent event of death (on or prior to Day 28), then time will be censored at the end of follow-up (Day 28), including those that were extubated prior to death.

5.4.1.5. Recovery or Improvement of at Least 2 Points Relative to Baseline of Sequential Organ Failure Assessment (SOFA) score up to Day 28

The SOFA score will be evaluated for participants in ICU with a SOFA score greater than 2 at baseline and analysed using a composite strategy to handle the intercurrent events as below.

Participants will meet the endpoint if they have an improvement of at least 2 points relative to baseline in SOFA score (derived where lower values indicate improvement) or they have recovered (discharged from ICU or investigator site for any other reason other than advanced facilitated care).

Intercurrent event	Response Status
Death	Non-responder
Discharge from ICU or Investigator Site to Advanced facilitated care	Non-responder
Discharge from ICU or Investigator Site for any other reason other than advanced facilitated care	Responder

In addition, change from baseline in SOFA score will be summarized for participants in ICU at baseline up to Day 28. This will be summarised using the trimmed means approach given in Section 5.4.2.4.

For the trimmed means, if >50% of the participants in ICU at baseline experience the intercurrent events listed above at any timepoint, then the data will be summarised up to that timepoint only.

If a participant experiences multiple intercurrent events, then the worst response status will be assumed.

5.4.1.6. Recovery or Improvement Relative to Baseline in Blood Oxygen Saturation (SpO₂)

Change from Baseline in SpO₂, calculated as daily average of all assessments, for participants who are not invasively mechanically ventilated at baseline. SpO₂ will be analysed using a composite strategy to handle the intercurrent events as below.

Participants will meet the endpoint if they have an improvement relative to baseline in SpO₂ (derived where higher values indicate improvement) or they have recovered (participant is discharged from investigator site for any other reason other than advanced facilitated care or participant is independent from supplementary oxygen and SpO₂ is missing).

Intercurrent event	Response Status
Death	Non-responder
Discharge from investigator site to advanced facilitated care	Non-responder
Use of Invasive Mechanical Ventilation	Non-responder
Discharge from Investigator Site for any other reason other than advanced facilitated care	Responder
Independence from supplementary oxygen and missing SpO ₂	Responder

In addition, change from baseline in SpO₂ will be summarized for participants not invasively mechanically ventilated at baseline up to Day 28. Participants who have SpO₂ recorded whilst on invasive mechanical ventilation will be set to missing. SpO₂ will be summarized for observed data and using a trimmed means approach as specified in the Section 5.4.2.4.

For the trimmed means, if >50% of the participants not invasively mechanically ventilated at baseline experience the intercurrent events listed above at any timepoint, then the data will be summarised up to that timepoint only.

If a participant experiences multiple intercurrent events, then the worst response status will be assumed.

5.4.1.7. Recovery or Improvement Relative to Baseline in Concentration of Inspired Oxygen (FiO₂)

Change from Baseline in FiO₂, calculated as daily average of all assessments. FiO₂ will be analysed using a composite strategy to handle the intercurrent events as below.

Participants will meet the endpoint if they have an improvement relative to baseline in FiO₂ (derived where lower values indicate improvement) or they have recovered (participant is discharged from investigator site for any other reason other than advanced facilitated care or participant is independent from supplementary oxygen and SpO₂ is missing). If FiO₂ is not recorded but Oxygen Flow Rate is, the FiO₂ will be calculated.

Intercurrent event	Response Status
Death	Non-responder
Discharge from investigator site to advanced facilitated care	Non-responder
Discharge from Investigator Site for any other reason other than advanced facilitated care	Responder
Independence from supplementary oxygen and missing SpO ₂	Responder

In addition, change from baseline in FiO₂ will be summarized for participants up to Day 28. FiO₂ will be summarized for observed data and using a trimmed means approach as specified in the Section 5.4.2.4.

For the trimmed means, if >50% of the participants experience the intercurrent events listed above at any timepoint, then the data will be summarised up to that timepoint only.

If a participant experiences multiple intercurrent events, then the worst response status will be assumed.

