5.1.4. Intercurrent Events

In general, the following may be considered intercurrent events if not part of the endpoint definition:

- Interruption or infusion stopped early and not completed
- Use of additional medications or changes to standard of care
- Death
- Discharge from ICU
- Admittance to ICU
- Start of Ventilation
- Termination of Ventilation
- Independence from supplementary oxygen
- Discharge from investigator site

The applicable intercurrent events for each endpoint will be highlighted within in the endpoint definition along with the strategy for handling them.

In general, unless otherwise specified, the handling strategy for all these intercurrent events will be based on a treatment policy approach; specifically, the effects estimated will be based on initial randomized treatment arm regardless of whether the participant had experienced an intercurrent event. If possible, data will continue to be collected after the occurrence of the intercurrent event, until the participant either completes the study or withdraws from the study before completion.

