5.4.1.8. Recovery or Improvement Relative to Baseline in SpO₂/FiO₂ Ratio

The ratio of SpO₂/FiO₂ will be calculated for each day using date-time matched values. Change from baseline in SpO₂/FiO₂ will be calculated as average of the daily

assessments, for participants who are not invasively mechanically ventilated. It will be analysed using a composite strategy to handle the intercurrent events as described in the individual endpoint sections. If a participant is a non-responder due to an intercurrent event for either SpO₂ or FiO₂ then they will be a non-responder for the ratio.

Participants will meet the endpoint if they have an improvement relative to baseline in SpO₂/FiO₂ ratio (derived where higher values indicate improvement) or they have recovered (the participant is discharged from investigator site for any other reason other than advanced facilitated care or the participant is independent from supplementary oxygen and SpO₂ is missing).

5.4.1.9. Oxygen-free Days up to Day 28

A participant is considered oxygen free on a day if they meet the definition in Section [5.3.1.5](#).

Intermittent data is expected after discharge from investigator site, therefore if participants have discontinued oxygen and have been discharged to a non hospitalised residence, they will be considered to be oxygen-free during the intermittent timepoints.

5.4.1.10. Ventilator-free Days up to Day 28

A participant is considered ventilator-free on a day if they meet the definition for being alive and not invasively mechanically ventilated in Section [5.4.1.3](#).

Intermittent data is expected after discharge from investigator site, therefore if participants have discontinued ventilation and have been discharged to a non hospitalised residence, they will be considered to be ventilation-free during the intermittent timepoints.

5.4.1.11. Time to Resolution of Pyrexia (>48h) up to Day 28

Time from dosing (days) to first resolution of pyrexia (defined as the first day of a >48-hour period with temperature below thresholds below) up to (and including) Day 28:

Location	Pyrexia Threshold	Core Temperature Equivalent
Forehead	>36.3°C	>37.8°C
Axilla	>36.6°C	>37.8°C
Sublingual region	>37.2°C	>37.8°C
Rectum or Tympanic membrane	>37.8°C	>37.8°C
Pulmonary artery branch	>37.8°C	>37.8°C
Bladder	>37.8°C	>37.8°C
Esophagus	>37.8°C	>37.8°C
Nasopharynx	>37.8°C	>37.8°C
Brain	>37.8°C	>37.8°C
Other	>36.3°C (Minimum Pyrexia Threshold)	>37.8°C

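### The Part 1 FiO₂ responder table gives no status to invasive ventilation started after baseline, so a newly intubated participant with a lower FiO₂ counts as recovered or improved

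*SAP*

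**What the plan says.** The SAP for Part 1 has three companion exploratory endpoints on oxygenation, each analysed as a binary response (5.4.2.2) by the adjusted logistic model of 5.2.2.

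- **FiO₂ (5.4.1.7).** The response rule is: "Participants will meet the endpoint if they have an improvement relative to baseline in FiO₂ (derived where lower values indicate improvement". Recovery, through ordinary discharge or independence from oxygen, also counts. The strategy is stated as "FiO₂ will be analysed using a composite strategy to handle the intercurrent events as below". The table that follows has four rows, and none concerns ventilation. A further rule says: "If a participant experiences multiple intercurrent events, then the worst response status will be assumed".
- **SpO₂ (5.4.1.6).** The table has the same kinds of row plus "Use of Invasive Mechanical Ventilation", scored as non-response. The endpoint is restricted: "for participants who are not invasively mechanically ventilated at baseline".
- **SpO₂/FiO₂ (5.4.1.8).** A participant who is a non-responder "due to an intercurrent event for either SpO₂ or FiO₂ then they will be a non-responder for the ratio".

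The general section on intercurrent events (5.1.4) lists "Start of Ventilation". Unless something else is specified, "the handling strategy for all these intercurrent events will be based on a treatment policy approach".

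**The concern.** A composite strategy builds bad outcomes into the response, so that they cannot be mistaken for benefit. Section 5.4.1.7 does this for death and for transfer to advanced facilitated care, but not for a new intubation. FiO₂ is a setting as well as a measure of need. A patient on high-flow oxygen at a high FiO₂ who deteriorates and is intubated may be run at a lower FiO₂ on the ventilator. Read literally, the rule reports that deterioration as recovery or improvement.

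At stake is whether one exploratory comparison can be interpreted. It is reported as an odds ratio with a confidence interval and p-value, next to two endpoints that score the same event the opposite way.

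**Working it through.** The plan states no figure for this point, so the check is of the rules and then of what they imply.

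**Step 1. The two tables side by side.**

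| Event | SpO₂ (5.4.1.6) | FiO₂ (5.4.1.7) |
|---|---|---|
| Death | Non-responder | Non-responder |
| Discharge to advanced facilitated care | Non-responder | Non-responder |
| Invasive mechanical ventilation | Non-responder | No row |
| Other discharge from site | Responder | Responder |
| Off supplementary oxygen, SpO₂ missing | Responder | Responder |

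**Step 2. Does another rule catch the event?** The worst-status rule in 5.4.1.7 ranks the statuses of events that have one. Intubation has none in that table, so the rule does not reach it. Section 5.1.4 then applies, and the observed FiO₂ is used. No other Part 1 section reclassifies the participant.

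**Step 3. Will the data exist?** Yes. Protocol 7.2.2 expects no SpO₂ value during mechanical ventilation. Protocol 7.2.3 and the Part 1 Schedule of Activities (1.3) place no such limit on FiO₂.

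**Step 4. Apply the rule to one participant.** Assume a baseline of 15 L/min. The only flow conversion printed is in the Part 2 SAP (6.3.2.3), borrowed here purely as an illustration: min(24 + (15 − 1) × 4, 100) = 80%. The participant is then intubated, alive and not discharged.

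| Ventilator FiO₂ | Rule as written | With a non-responder row for ventilation started after baseline |
|---|---|---|
| 40, 50, 60 or 70% | Responder | Non-responder |
| 80 or 100% | Non-responder | Non-responder |

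A participant already ventilated at baseline gets the same result under both rules if the row is limited in this way.

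**Step 5. The same participant elsewhere.** SpO₂: non-responder, by the ventilation row. SpO₂/FiO₂: non-responder, inherited from SpO₂. Ordinal scale: intubation is category 6 (5.1.6.2), and 5.3.1.4 counts category 5 or above as respiratory failure.

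**Step 6. Can a between-arm effect be signed?** Let d be the excess intubation rate in one arm. Let q be the FiO₂ response rate among those extra intubated participants, and r the rate they would have had without intubation. Under the rule as written, that arm's response rate changes by d × (q − r). None of the three is in the documents. With assumed values d = 0.05 and q = 0.40 to 0.70:

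- r = 0: 0.05 × 0.40 to 0.05 × 0.70 = +2.0 to +3.5 percentage points
- r = 0.80: 0.05 × (0.40 − 0.80) to 0.05 × (0.70 − 0.80) = −2.0 to −0.5 percentage points

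The sign depends on r, so the direction is open.

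**The case against.** The strongest defence is that the tables differ for a reason. SpO₂ is not expected during invasive ventilation, and any value recorded then is set to missing, so that endpoint needs a ventilation rule. Its population also excludes participants ventilated at baseline. FiO₂ is collected on the ventilator and its endpoint includes those participants, so the SpO₂ row copied unchanged would make all of them non-responders while they remained ventilated. Treatment policy is the declared default, and worsening to ventilation is captured by other endpoints: new invasive ventilation or death and the time to it, ventilator-free days, clinical status, and the primary endpoint.

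This explains why the row could not be copied as it stands. It does not make the result sensible in a section that declares a composite strategy, and a row limited to ventilation started after baseline avoids the difficulty. That the other endpoints capture intubation limits the harm but does not remove the contradiction.

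The objection does stand against two stronger inferences that a reader might draw. The first is that the estimate is biased toward the arm with more intubations. That holds only against a definition in which intubation is always failure; within the endpoint as written, step 6 shows that the sign is undetermined. The second is a count of affected participants. This would need the share intubated after baseline and the share of those with a lower FiO₂, and neither is given. Participants who die are already non-responders, and 5.4.1.7 names no assessment day for the response.

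The Amendment 3 summary of changes says that the dropped exploratory endpoints will not be reported, but that entry describes Part 2. The Part 1 SAP still defines this endpoint and lists it for analysis.

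**Conclusion.** The gap is real and follows from the text alone. A participant not invasively ventilated at baseline who is intubated and has a ventilator FiO₂ below baseline is an FiO₂ responder, unless death or discharge to advanced facilitated care applies. That makes the comparison less sensitive to worsening and inconsistent with SpO₂ and SpO₂/FiO₂.

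Its reach is modest. The endpoint is exploratory, may or may not be analysed (5.4), and no primary or secondary result depends on it. The Part 2 FiO₂ table (Part 2 SAP, 4.4.1.9) also lacks a ventilation row, but Part 2 summarises observed values and trimmed means and has no FiO₂ responder endpoint, so the point is confined to Part 1. The 80% baseline is an illustration; the conclusion needs only that some newly intubated participants have an FiO₂ below their baseline.

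**What to change.** Add one row to the 5.4.1.7 table: *Use of invasive mechanical ventilation on the day assessed, for participants not invasively ventilated at baseline: Non-responder.* Take baseline ventilation status from 5.1.2, and keep participants ventilated at baseline on observed FiO₂. The words *on the day assessed* matter. Without them, the worst-status rule could make a participant who was intubated, extubated and sent home a permanent non-responder.

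Protocol 8.4.2 states that the Part 1 primary endpoint has already been analysed, so the changed rule should not replace the definition as written. Report it beside that definition, labelled as added after those results were known. The data are already collected. The cost is one extra derivation and one extra output for an exploratory endpoint.
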